6.1 POWER ANALYSIS AND BORROWING DATA FROM NICHE-TRIAL ACTIVE TRIAL ARM RESULTS

In a pilot study of 30 patients of whom 20 were randomized to active NBS-rTMS and 10 to sham-rTMS, 84% of the active NBS-rTMS group and 50% of the sham rTMS group attained clinically significant improvement of at least 5 points on the Fugl-Meyer score [Harvey RL 2009, Harvey RL, unpublished].

Similarly, in the completed multi-centre trial (NICHE-trial, NCT02089464) of 199 subjects using the same trial device but different sham coil design, 72% of subjects with ischemic stroke receiving active NBT-rTMS attained clinically significant improvement of at least 5 points on the Fugl-Meyer score [Harvey RL, manuscript in preparation] while the average expectation of NICHE trial site principal investigators of subjects improving was 36%.

Based on this data and sample size calculations utilizing significance level of 0.05 for p, we estimate that enrolling 60 patients need to be recruited to the present study to rule out the null hypothesis that there is no difference between active NBT-rTMS and sham-rTMS with 81% power. This assumption is based on the pilot study finding of 33% difference in responder rate between groups in favour of the NBS-rTMS group and 36% difference in the actual vs expected responder rate in patients with ischemic stroke in NICHE. However, since the active treatment arm of the present trial and the active trial arm of NICHE are treated in a completely identical manner (the same NBT device, same active rTMS protocol, the same standardized occupational therapy protocol as in NICHE, the same number of therapy sessions in the same schedule at the same trial sites, etc) this allows pooling of the data obtained in the NICHE active trial arm to the data obtained in the active trial arm in the present trial. As in NICHE there were 88 subjects with ischemic stroke receiving active NBT-rTMS. Combining their data with that of the present trial will lead into a trial population of approximately 118 subjects receiving active treatment (88 from NICHE + 30 from the present trial) and approximately 30 subjects receiving sham treatment (all from the present trial). The study power in this population is sufficient to rule out the null hypothesis with 96% power.

The statistical analysis of the present trial will be performed in two phases. The Bayesian analysis of the E-FIT data combined with data borrowed from the active trial arm of the previously completed NICHE trial (NCT02089464) will be the primary efficacy analysis. Non-Bayesian analysis of the E-FIT trial data only will be performed to demonstrate robustness of the result. Detailed methodology for the analyses is described in a separate statistical analysis plan (Document NX103391 EFIT Statistical Analysis Plan, version 1.0, dated 06 August 2018).

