6.0 ANALYSIS PLAN

The results of functional motor tests at end of rehabilitation (5-10 days post treatment) and at 1, 3 and 6 months after the end of rehabilitation will be compared to the results obtained at baseline to determine the functional recovery if any that has occurred. The results of patients randomized into separate groups will be compared to each other to determine the effect of rTMS.

The primary analysis population will be the intent-to-treat (ITT) population. In addition, a separate analysis will be conducted on the per protocol (PP) population.

Primary outcome measure for the trial is the Upper-extremity Fugl-Meyer score.

The beneficial effect of 1Hz NBS guided rTMS will be established if a statistically significantly greater proportion of patients receiving NBS-rTMS attain clinically important improvement in the primary outcome measure than patients receiving sham-rTMS between baseline and 6 months post-treatment.

The size of the treatment effect will be measured by the odds ratio parameter which is defined as

$$OR = \frac{P_{TRT} / (1 - P_{TRT})}{P_{REF} / (1 - P_{REF})}$$

where P_{TRT} and P_{REF} denote the proportion of subjects with clinically significant change from baseline in Fugl-Meyer score, in the treatment and reference groups respectively.

The null hypothesis is H_0 : OR = 1 and the two-sided alternative hypothesis is H_1 : $OR \neq 1$.

The proportion of responders in each treatment group will be summarized, along with the estimated odds ratio, the 95% confidence interval for OR, and the Wald Chi-square test p-value. The primary analysis will be performed on the ITT, and on the PP population as a sensitivity analysis.

Secondary outcome measures for the trial are ARAT test, , NIHSS, and EQ-5D.

Descriptive statistics will be summarized by treatment and visit. Absolute difference (in points) in improvement will be summarized for both treatment groups between baseline and 5-10 days and 1, 3 and 6 month follow-up visits and the treatment groups compared via a two-way ANOVA.

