6.3 ANALYSIS POPULATIONS

Intent-to-Treat (ITT) Population

The ITT population will consist of all randomized subjects. Subjects in the ITT population will be summarized and analyzed in the treatment group to which they were randomized, regardless of the treatment they actually received.

Per Protocol (PP) Population

The PP population will consist of all subjects who were randomized, received study treatment, and had no major protocol violations.

If a subject suffers a new stroke during the trial and the new stroke affects the motor function of the limb being treated in the study, only the outcome assessment data collected prior to the new stroke will be used for PP Population analysis. The sponsor will review the new strokes and determine if it affects the motor function of the limb.

Safety Population

The Safety population will consist of all subjects who received study treatment. Subjects in the safety population will be summarized and analyzed according to the treatment they actually received, regardless of whether or not they were randomized to receive that treatment.

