6.4 STRATA AND COVARIATES

The primary efficacy analysis will be stratified by length of time after stroke (3-6 months vs. 6-12 months).

Additional covariate analyses will model the primary endpoint (a binary response of UEFM score improvement), absolute changes (in points) in the tests of motor function (UEFM, and ARAT) using hours of occupational therapy outside the trial and overall hours of therapy (occupational, physical, and home exercise) as covariates during treatment phase and over the entire 6 months of follow-up.

All covariate analysis will be performed for both ITT and PP population.

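### Two different analyses are called primary: the randomised ITT odds-ratio test in 6.0 and the Bayesian analysis borrowing NICHE active-arm patients in 6.1. The summary, 3.1, 6.0 and 6.4 were not reconciled with 6.1

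*Combined protocol and SAP*

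**What the plan says.** Section 6.0: "The primary analysis population will be the intent-to-treat (ITT) population". Its test is of an odds ratio of 1, reported with a 95% confidence interval and a Wald chi-square p-value, and "The primary analysis will be performed on the ITT, and on the PP population as a sensitivity analysis". Section 6.3 adds: "The ITT population will consist of all randomized subjects".

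The summary, 3.1 and 6.0 share one success rule: a statistically significantly greater proportion of responders (at least 5 points on the upper-extremity Fugl-Meyer) on active than on sham at 6 months. Section 6.5 sets a two-sided 0.05 level.

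Section 6.1 states that the Bayesian analysis of E-FIT data "combined with data borrowed from the active trial arm of the previously completed NICHE trial (NCT02089464) will be the primary efficacy analysis". It continues: "Non-Bayesian analysis of the E-FIT trial data only will be performed to demonstrate robustness of the result". Borrowing is into the active arm only: 88 NICHE plus about 30 E-FIT patients on active, against about 30 on sham, all from E-FIT. Stated power is 81% for E-FIT alone and 96% for the combined set. On method: "Detailed methodology for the analyses is described in a separate statistical analysis plan".

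Section 6.4: "The primary efficacy analysis will be stratified by length of time after stroke". It does not say which of the two analyses is meant or how NICHE patients would be stratified.

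**The concern.** One efficacy claim has two definitions of its primary analysis, and the only written success rule fits the definition that 6.1 demotes to robustness. A Wald p-value in all randomised subjects is not a Bayesian analysis with 88 external patients.

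The mismatch matters because the borrowing is one-sided. If E-FIT patients respond less often than NICHE patients did, the borrowed data raise the active rate but not the sham rate, and the analysis can favour the device when the randomised arms do not differ. If they respond more often, it works against the device. If the text is not settled before unblinding, either result could be presented as the primary one.

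**Working it through.** **Inputs.** 30 v 30 (5.2.3); two-sided 0.05 (6.5); NICHE ischemic active rate 72% of 88 and site investigators' expected rate 36% (6.1); pilot 84% v 50% (6.1); NICHE sham rate 65% (1.1). Assumed: NICHE count 63/88 (0.72 × 88 = 63.4; 63/88 = 71.6%), fixed borrowing weights and a 1.96 cut-off. The weights are full (88 patients), half (44) and 15 effective patients.

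**1. The plan's power.** Power = Φ[(d − 1.96·s0)/s1], with s0 the pooled and s1 the unpooled standard error. At 72% v 36%, d = 0.36:

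- 30 v 30: s0 = 0.1287, s1 = 0.1200, giving Φ(0.898) = 81.5% (plan: 81%).
- 118 v 30: s0 = 0.0977, s1 = 0.0969, giving Φ(1.739) = 95.9% (plan: 96%).
- 74 v 30 (half weight): s0 = 0.1053, s1 = 0.1020, giving Φ(1.507) = 93.4%.

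At 84% v 50% the first two are 81.6% and 96.1%. Both stated figures reproduce, but the 96% needs all 88 NICHE patients at full weight.

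**2. One data set, different verdicts.** z = ln(OR)/√(sum of reciprocal cell counts). Suppose E-FIT gives 18/30 active and 14/30 sham.

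- E-FIT alone: OR = (18×16)/(12×14) = 1.71, SE 0.522, z = 1.03, p = 0.30.
- Half weight, 49.5/74 active: OR = (49.5×16)/(24.5×14) = 2.31, SE 0.442, z = 1.90, p = 0.058.
- Full weight, 81/118 active: OR = (81×16)/(37×14) = 2.50, SE 0.416, z = 2.20, p = 0.028.

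**3. How often the two disagree on a finding for active.** Exact enumeration of two Binomial(30, p) arms with the Wald test (0.5 added to all cells if any is zero):

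| True rates | Full | Half | 15 effective |
|---|---|---|---|
| 72% v 36% | 14.5% | 12.6% | 7.3% |
| 72% v 50% | 23% | 18% | 8% |
| 84% v 50% | 12% | 8% | 3% |

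In the first two rows the borrowed analysis is nearly always the significant one. In the third it is mostly E-FIT alone.

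**4. No true effect: false findings for active (nominal 2.5%).** Same enumeration, same response rate in both E-FIT arms:

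| Common rate | Full | Half | 15 effective | E-FIT alone |
|---|---|---|---|---|
| 72% | 1.5% | 1.6% | 1.6% | 2.0% |
| 65% | 6.0% | 4.5% | 2.9% | 2.2% |
| 60% | 12.7% | 8.0% | 4.1% | 2.4% |
| 50% | 35.3% | 20.1% | 7.2% | 2.6% |

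Two-sided error at full weight exceeds 5% below a common rate of about 66.5%, and again at about 80% (5.2%, of which 5.1 points favour sham).

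**5. Power of each candidate, same enumeration (full / half / E-FIT alone).** 72% v 36%: 96.5 / 94.7 / 82.1%. 72% v 50%: 61.1 / 57.3 / 40.9%. 84% v 50%: 74.9 / 78.9 / 80.4%.

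**The case against.** The strongest reply is that 6.1 already settles the order: it names both analyses, calls the Bayesian one primary and the other a robustness check. That stands. A reader might infer from 6.0 that the protocol gives no ranking at all, and the documents do not support that. What remains is that the sections holding the success rule and the test were left as they were.

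Second, the ITT definition can be read as settling which E-FIT patients enter, and in which arm, with NICHE coming in as external information. That reading is possible for 6.3, but it does not reconcile the Wald test in 6.0 with a Bayesian primary analysis.

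Third, the weight, prior, threshold, handling of strata and a rule for discordance may all be in the separate SAP, which 6.1 cites by number, version and date. This also stands. They are absent from the documents supplied, not shown to be absent from the plan. Even a complete SAP would leave 6.0 and 6.1 in conflict.

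Fourth, 6.1 states that device, rTMS protocol, therapy, schedule and sites match NICHE, and 1.1 calls the population otherwise identical apart from stroke type. This makes a shift in response less likely but does not exclude it. At the NICHE rate of 72% borrowing causes no inflation. The 35.3% figure needs full weight and a fall of about 22 points.

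**Conclusion.** The inconsistency is in the text and needs no assumption: two analyses are called primary, and the stated success rule belongs to the one that 6.1 treats as robustness. The choice can change the conclusion, with 7.3% to 14.5% disagreement at 72% v 36% across the weights examined.

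A reader might go further and infer that the trial's false-positive rate is inflated, or that borrowing always helps the device. Neither follows. The borrowing weight and success threshold are not in the documents, so the plan's error rate cannot be stated; dynamic borrowing or a stricter threshold could lower the figures above. The direction also depends on the E-FIT response rate: near 80% the error turns against the device, and at 84% v 50% E-FIT alone has the higher power.

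The reference rates are weak. The 36% is an expectation, not an observation. The 65% NICHE sham rate is not given for ischemic stroke alone, and the sponsor believes that coil may have been active. The 50% pilot sham rate comes from 10 patients.

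**What to change.** Before unblinding, state one primary analysis and one success rule consistently in the summary, 3.1, 6.0, 6.1 and 6.4, and align the separate SAP. Either option is acceptable.

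- **(a) Keep 6.1.** Amend the summary, 3.1, 6.0 and 6.4 so that the Bayesian analysis and its success threshold decide. State or cross-reference the borrowing weight or prior, and how the time-since-stroke stratification applies to NICHE patients. Report the false-positive rate over E-FIT response rates of 50% to 80%. Restate the 96% power for the weight actually used. Say what is concluded if the randomised E-FIT-only comparison disagrees.
- **(b) Make the randomised E-FIT ITT odds ratio primary**, with the borrowed analysis supportive. This rests on the plan's own 81% power, which was reproduced here for the unstratified comparison. It reverses an explicit sponsor choice and loses power when the active response is near the NICHE rate: about 82% against 95–96% at 72% v 36%, and 41% against 57–61% at 72% v 50%.

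Neither option needs extra patients or visits, since both analyses are already planned. Option (a) costs redrafting and a calculation of operating characteristics; option (b) costs redrafting and the power shown.

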6.2 ANALYSIS SCHEDULE

No interim analyses will be performed for efficacy. Final analysis including analysis of safety and efficacy will be performed once 60 subjects have completed the trial (completed visit #24).

6.3 ANALYSIS POPULATIONS

Intent-to-Treat (ITT) Population

The ITT population will consist of all randomized subjects. Subjects in the ITT population will be summarized and analyzed in the treatment group to which they were randomized, regardless of the treatment they actually received.

Per Protocol (PP) Population

The PP population will consist of all subjects who were randomized, received study treatment, and had no major protocol violations.

If a subject suffers a new stroke during the trial and the new stroke affects the motor function of the limb being treated in the study, only the outcome assessment data collected prior to the new stroke will be used for PP Population analysis. The sponsor will review the new strokes and determine if it affects the motor function of the limb.

Safety Population

The Safety population will consist of all subjects who received study treatment. Subjects in the safety population will be summarized and analyzed according to the treatment they actually received, regardless of whether or not they were randomized to receive that treatment.

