2.2. RISKS

Single-pulse TMS

Localization of the muscle representation area which will be subsequently the target location for delivering 1Hz rTMS therapy will be performed using the NBT device in a single pulse mode. Single pulse TMS has been studied extensively and been established to be safe in practically all subjects [Bridgers 1991; Bridgers and Delaney 1989]. It was judged by a panel of experts with FDA representation at an NIH Consensus Conference in June 1996 to be a **nonsignificant risk application** [Hallett et al. 1999; Wassermann 1996]. No serious adverse events related to single-pulse stimulation have been reported to Nexstim by any user of the study device or earlier product generation.

1Hz rTMS

In the report of the NIH Consensus Conference cited above [Wassermann 1996] rTMS was recognized to be associated with potentially more frequent (although still rare) adverse effects than single-pulse TMS. The frequency of adverse effects was noted to increase in parallel with the frequency (Hz) and intensity (% of motor threshold) of the rTMS trains used. The workshop issued safety guidelines where for 1Hz rTMS trains of >1800 pulses given at 100 or 110% of motor threshold were considered safe. These guidelines have been reassessed and updated with no change to the evaluation of safety of the 1Hz rTMS paradigm [Rossi 2009]. In the present study 1Hz trains of 900 pulses at 110% of motor threshold targeting the healthy brain hemisphere will be utilized in patients at least 3 months from stroke. The protocol falls within the safety guidelines.

In the clinical trials investigating the efficacy and safety of rTMS paradigms similar to the one used by the NBT in the patients with stroke, no serious adverse events have been reported in the 27 studies in 2598 patients with stroke in 2005-2016 (Boggio 2006 Mally J and Dinya E,2008, Dafotakis M 2008, Fregni F 2006, Khedr EM 2008, Kirton A 2008, Liepert J 2007, Mansur CG 2005, Nowak DA 2008, Takeuchi N 2005, Takeuchi N 2008(a), Takeuchi N 2008(b), Khedr EM 2009, Emara T, 2010, Kakuda W 2011 (a), Kakuda W 2011 (b), Thielig S 2011, Kakuda W 2011 (c), Kakuda W 2012, Sung W 2013, Abo M 2013, Higgins 2013, Kim, 2014. Rose 2014 Cha H 2015, Zheng C 2015, Kakuda W 2016).

Further, no serious adverse events have occurred in the studies where NBS-guided rTMS has been used (a total of 3813 rTMS sessions in 224 patients with stroke) [Bashir S 2010 (b), Harvey RL,

CONFIDENTIAL

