Seizure activity is a theoretical risk of TMS. Although, single pulse TMS has not caused seizure activity in healthy volunteers, seizures have been produced by single-pulse TMS in several patients with large cerebral infarcts or other structural lesions [Fauth et al. 1992; Homberg and Netz 1989; Kandler 1990]. Epilepsy patients without gross lesions may also be at a minor degree of risk from single pulse TMS. For example, in a series of studies by Hufnagel and colleagues, single-pulse TMS was occasionally able to induce seizures or activate epileptic electroencephalography (EEG) foci [Hufnagel et al. 1990a; Hufnagel et al. 1990c]. In this study slow frequency trains of stimulation were used. In the current study we propose to use single pulse stimuli with a variable interstimulus interval. However, these results may not apply in patients in whom epilepsy is medically controlled. To wit, Tassinari et al [Tassinari et al. 1990] found that TMS did not incite seizure activity in a cohort of patients receiving anti-epileptic therapy. Subjects with a personal history of epilepsy will be excluded from this study.

rTMS has been reported to cause seizures in at least 7 individuals in whom frequencies of 3Hz or higher have been utilized [Wassermann 1996].

In the clinical trials investigating the efficacy and safety of rTMS paradigms similar to the one used by the NBT in the patients with stroke, no seizures have been reported in the 27 studies in 2598 patients with stroke in 2005-2016 (Boggio 2006 Mally J and Dinya E,2008, Dafotakis M 2008, Fregni F 2006, Khedr EM 2008, Kirton A 2008, Liepert J 2007, Mansur CG 2005, Nowak DA 2008, Takeuchi N 2005, Takeuchi N 2008(a), Takeuchi N 2008(b), Khedr EM 2009, Emara T, 2010, Kakuda W 2011 (a), Kakuda W 2011 (b), Thielig S 2011, Kakuda W

2011 (c), Kakuda W 2012, Sung W 2013, Abo M 2013, Higgins 2013, Kim, 2014. Rose 2014 Cha H 2015, Zheng C 2015, Kakuda W 2016).

Further, no seizures have occurred in the studies where NBS-guided rTMS has been used (a total of 365 rTMS sessions in 25 patients with stroke) [Bashir S 2010 (b), Harvey RL, 2013, Harvey, RL, manuscript in preparation]. Similarly, no seizures occurred in the NICHE multicentre trial in the 3448 therapy sessions performed in 199 patients using the same trial device and protocol as the present trial.

Auditory Changes

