5.2. VISIT SCHEDULE

The study will be performed over 24 to 29 sessions:

- 1) Visit 1(Screening visit): Baseline = 3-12 months after the stroke. The purpose of this visit is to obtain informed consent for the study (if not previously obtained) and to screen subjects for inclusion and exclusion criteria.
- 2) Visit 2: Baseline assessment. The purpose of this visit is to establish the baseline of injury, motor status and NBS parameters (Localization of cortical motor representation area of the target muscle to which therapeutic rTMS will be subsequently delivered, see appendix A). Subjects will also undergo a structural MRI. The subject will then be randomized to either rTMS or to sham treatment. The baseline visit may if necessary take place on 2 separate days.

- 3) Visits 3-20: During these visits the patient will undergo standardized task-oriented motor rehabilitation of the hand. In addition the patient will receive the rTMS therapy according to the protocol of the group she/he was randomized into during visit 1. The visits will take place during a 6 week period, three visits per week. During each week the visits will take place each on a separate day and a maximum of two visits will take place on consecutive days.
- 4) Visit 21: End of the task-oriented motor rehabilitation. The purpose of the visit is to establish the extent of recovery that has occurred during the rehabilitation. The visit will take place 5-10 days after the last rTMS/rehabilitation session and includes functional motor testing).1-2 visits may be needed to complete assessment.
- 5) Visit 22: 1month (±5 days) after the end of the rehabilitation therapy. The purpose of the visit is to determine whether any changes in motor function have occurred within 1 month of ending therapy. The assessment includes functional motor testing. 1-2 visits may be needed to complete assessment.
- 6) Visit 23: 3 months (±5 days) after end of the rehabilitation therapy. The purpose of this visit is to determine whether any changes in motor function or NBS parameters have occurred within 3 month of ending therapy. The assessment includes functional motor testing. In patients experiencing a new stroke, only the data prior to the event will be used in the analysis. 1-2 visits may be needed to complete assessment.

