6.7 SAFETY ANALYSES

The Safety Population will be used for all analysis, summaries, and listings of safety data.

Adverse Events

All reported terms (investigator descriptions) for AEs will be coded using the most recent version of the Medical Dictionary for Regulatory Activities (MedDRA v16.0) and summarized with frequencies and percentages by treatment group, system organ classification, and preferred term.

Note that subjects experiencing AEs are counted at most one time per preferred term and at most one time per system organ class, at the highest recorded severity and causality. Events without recorded relationship or causality are summarized as severe or definitely related.

The number and percentage of subjects in the following categories will be summarized by group and overall: subjects with AE, TEAE, SAE, TESAE, UADE, DRAE, TEAE resulting in study discontinuation, and deaths.

The following tables will also be presented:

- All TEAEs
- SAEs and TESAEs
- TEAEs by severity
- TEAEs leading to premature discontinuation of study treatment.

Separate data	listings	W1II	be	presented	for	all	AEs	and	SAES.
---------------	----------	------	----	-----------	-----	-----	-----	-----	-------

Unanticipated Adverse Device Events (UADE)

A UADE is defined as any AE that is definitely related to the study device. All UADEs will be summarized by System Organ Class and Preferred Term. A listing of UADEs will also be provided.

Device-Related Adverse Events (DRAE)

A DRAE is defined as any AE that is possibly, probably, or definitely related to the study device. All DRAEs will be summarized by System Organ Class and Preferred Term. A listing of DRAEs will also be provided.

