6.7.1 Primary Safety Analysis

The use of study treatment will be considered safe if the proportion of SAEs in the active rTMS group is not statistically significantly higher than that in the sham group. Number of subjects with SAEs and TESAEs will be summarized by group and compared using a Chi Square test.

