6.7.2 Use of Safety results in future labeling

A summary of SAE, UADE and DRAE will be included in future labelling of the NBT device.

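### Device events from Visit 2 mapping in patients who leave before Visit 3 are missing from the planned safety tables, listings and labelling summary

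*Combined protocol and SAP*

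**What the plan says.** All references are to the combined protocol and SAP.

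- **Safety set.** Section 6.3: "The Safety population will consist of all subjects who received study treatment". Subjects are grouped by the treatment they actually received.
- **Scope.** Section 6.7 opens: "The Safety Population will be used for all analysis, summaries, and listings of safety data". The listings of all AEs and SAEs promised later in 6.7 fall under that sentence.
- **Study treatment.** The term has no formal definition. Section 6.7.1 uses it for the randomised stimulation: "The use of study treatment will be considered safe if the proportion of SAEs in the active rTMS group is not statistically significantly higher" than in the sham group. Stimulation is given at Visits 3-20, for which section 5.2 says: "During these visits the patient will undergo standardized task-oriented motor rehabilitation of the hand", with rTMS or sham in addition.
- **Device exposure before that.** Section 2.2 says that localising the target area "will be performed using the NBT device in a single pulse mode". Sections 5.2 and 5.2.2 and Appendix A place this mapping and thresholding at the baseline visit (Visit 2). The Visit 2 entry then says: "The subject will then be randomized to either rTMS or to sham treatment". The Visits 3-20 entry instead puts randomisation at visit 1; the two must be reconciled, but both precede Visit 3.
- **Event definitions and use.** Section 6.7 defines DRAEs and UADEs by their relation to the study device. Section 6.7.2: "A summary of SAE, UADE and DRAE will be included in future labelling of the NBT device".
- **Collection.** Section 7.0 collects adverse events throughout the study.

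**The concern.** Exposure to the device begins one visit before the population that is meant to describe its safety. A patient who has an event during mapping and withdraws, whether before or after randomisation, has received no study treatment and so belongs to no set that produces safety output.

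The safety objective in section 3.2 is the safety of using the study device, and it asks for all SAEs, UADEs and DRAEs. It is not confined to rTMS sessions. Mapping precedes therapy for every patient, so it is part of using the system. The exclusion may also depend on the outcome, because the event itself can be the reason for leaving. Section 4.1 allows lost or withdrawn patients to be replaced, and section 6.2 waits for 60 completers, so such a patient could be replaced without the event appearing in the final safety report.

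What is at stake is the completeness of the device-event counts, above all those that go into labelling.

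**Working it through.** The plan states no figure on this point, so there is none to reproduce. The check has two parts: follow one patient through the rules, then size the gap.

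**1. One patient through the rules.** Suppose a patient is mapped at Visit 2, has an event that is possibly device-related, and withdraws before Visit 3.

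- Recorded? Yes (section 7.0, collection throughout the study).
- A DRAE? Yes (section 6.7: possible relation to the study device suffices).
- In the Safety population? No (section 6.3). Reading study treatment to include the rehabilitation does not help, since that also starts at Visit 3. A patient who was only mapped also has no treatment received by which to be grouped.
- In a table or listing under 6.7? No (its opening sentence).
- In the labelling summary? Not if that summary is built from the 6.7 outputs, and no other source is named.

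If the same patient goes on to Visit 3, the event stays in the Safety population as an AE, SAE or DRAE. The gap is therefore limited to those who leave early.

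**2. How many randomised patients could this be?** The documents give no count of patients mapped but never treated. NICHE session counts give a rough ceiling.

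- Inputs: 3448 sessions in 199 patients (section 2.2); 18 sessions per patient (Appendix B). Section 6.1 says the active arms of the two trials had the same number of sessions; applying 18 to all 199 patients is an assumption.
- Planned sessions: 199 × 18 = 3582. Missed: 3582 − 3448 = 134.
- If every missed session belonged to a never-treated patient: 134 / 18 = 7.4 patients, and 7.4 / 199 = 3.7%.
- Scaled to this trial: 60 × 134 / 3582 = 2.2, about 2 patients.

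The true number could be 0. Patients mapped but not randomised come on top, and the documents give no number for them.

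**3. Chance that at least one event goes untabulated.** With w early leavers, each with event probability r at mapping, it is 1 − (1 − r)^w, and the expected number of lost events is w × r. The documents give neither w nor r; both are assumed.

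| w | r = 1% | r = 5% | r = 10% | r = 20% |
|---|---|---|---|---|
| 1 | 1% | 5% | 10% | 20% |
| 2 | 2% | 9.8% | 19% | 36% |
| 6 | 5.9% | 26.5% | 46.9% | 73.8% |

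With w = 2, expected lost events run from 2 × 0.01 = 0.02 to 2 × 0.20 = 0.40. As an illustration of what one lost event does: 1 / 60 = 1.7% would be reported as 0%.

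**The case against.** The strongest reply is that a treated, as-received safety set is standard and suits a trial of rTMS therapy, that the numbers are tiny, and that oversight is intact. Much of this stands.

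- **Oversight.** A reader might infer that these events disappear altogether. They do not. Under section 7.0, SAEs go to the IRB and sponsor within 24 hours, other AEs go to IRB continuing review and the DSMB, and the DSMB assesses every AE for relation to the device or procedure. That section also promises SAE counts by event and by patient without naming a population. This leaves the handling of SAEs unclear against 6.7; it provides no output for non-serious device events.
- **The safety rule.** A reader might infer that the comparison in 6.7.1 is distorted. It is not: it compares arms, treated subjects are a reasonable basis for it, and a patient never randomised has no arm.
- **Size.** A reader might count the mapping exposure of all 60 patients as lost. Only that of early leavers is. The NICHE sessions are described as performed in 199 patients, which read literally means that none was untreated. An upper confidence limit for 0 events in 60 would describe the precision of the sample and would be the same with a correctly defined set.
- **Seizure risk.** Section 2.2 does say that "seizures have been produced by single-pulse TMS in several patients with large cerebral infarcts or other structural lesions". A reader might carry that over to this trial. But entry requires ischemic stroke with arm and hand stages 3-6, not a large infarct, and only the healthy hemisphere is mapped. Section 2.2 also says that no serious single-pulse event has been reported to the manufacturer by users of the study device or its earlier generations. The passage shows that mapping is not treated as free of risk. It gives no rate for this population.

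None of this supplies a table or listing for a device event in a patient who was mapped and never treated.

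**Conclusion.** The gap is real in the rules and small in likely effect. As sections 6.3 and 6.7 are written, an AE, SAE, DRAE or UADE from mapping in a patient who leaves before Visit 3 is collected and reviewed but enters no planned safety output, nor the labelling summary. Probably 0 to 2 randomised patients are affected, plus an unknown number mapped but not randomised. The upper figure assumes that all missed NICHE sessions belonged to never-treated patients on an 18-session schedule.

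The conclusion rests on reading study treatment as what begins at Visit 3, which the protocol's usage supports but no definition confirms. The detailed SAP cited in section 6.1 was not available and may define the set differently; the protocol text would still need to agree with it.

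Severity is minor to moderate. The documents do not support calling it a must-fix, and replacing the Safety population itself is more than is needed.

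**What to change.** - **Section 6.3:** keep the treated Safety population for the by-arm tables and the 6.7.1 comparison, and define study treatment. Add a device-exposed set: all subjects who received at least one TMS pulse with the NBT system, randomised or not.
- **Section 6.7:** add a listing and a summary of AEs, SAEs, DRAEs and UADEs in that set, from the first mapping pulse to first study treatment, not attributed to an arm. Limit the opening sentence so that it does not exclude this output. Note that events in patients who went on to treatment also appear in the by-arm tables, so that no one is counted twice.
- **Section 6.7.2:** include the mapping-phase summary in the labelling summary.
- **Section 5.2:** reconcile the two statements on when randomisation takes place.

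The cost is some wording, one extra listing and one extra summary. No new data, visits or patients are needed, since adverse events are already collected throughout the study. The downside is that the reported device-event rate may be slightly less favourable.
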